5. RESEARCH ABSTRACT

Please provide a brief description in LAY language (understandable to an 8th grade student) of the aims of this project.

Clinicians who stigmatize people at risk of or living with HIV provide worse HIV testing, treatment, and linkage to care services to these populations. To date, the vast majority of stigma-reduction interventions for clinicians have occurred in single healthcare facilities. We propose to deliver evidence-based stigma reduction tools through a popular teletraining platform for clinicians, Project ECHO[®]. Project ECHO[®] (Extension for Community Healthcare Outcomes) has trained, supported, and empowered 70,000+ clinicians to provide a wide range of specialty care services in 37+ countries globally, including HIV testing, prevention, and linkage to care. It uses a "hub and spoke" model wherein non-specialists in community setting "spokes" learn from and collaborate with specialists at academic "hubs" via

videoconferencing technology (i.e., Zoom software). By delivering stigma-reduction tools through Project ECHO®, we could substantially extend the reach of stigma-reduction interventions for clinicians.

There are four phases of our project:

- **Phase 1:** We will explore experiences of stigma among people at risk of and living with HIV using Photovoice, a qualitative data collection technique involving photography and story-telling (n=35).
- **Phase 2:** We will explore clinicians' perspectives on an intervention to address stigma through online focus groups (n=40).
- **Phase 3:** We will conduct a brief pre-test of our intervention protocol with a small sample of clinicians (n=5).
- **Phase 4:** We will pilot test our intervention protocol among clinicians, comparing it to two control conditions (n=78). Our intervention materials will include Photovoice presentations created by participants in Phase 1 of the study. Importantly, these presentations will be screened to ensure that they do not contain identifying information (e.g., faces).

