3. *Participants randomized to our intervention (n=26) will complete Project ECHO® for HIV Prevention intervention with added evidence-based stigma reduction tools. Participants will meet with the Project ECHO® Hub specialists and their learning community on a bi-weekly basis for 90 minutes over the course of 9 months. Their Hub specialists will include the infectious disease, mental/behavioral health, and family medicine specialists, as well as the stigma expert and community representative. The stigma expert and community representative will monitor discussion and address stigmatizing content (e.g., via discussion and didactic training), thereby shaping social norms. The Hub specialists will be joined periodically by guest speakers with expertise in infectious disease, pharmacology, case management, and other clinical topic areas as well as stigma and key population communities. Each session will feature a didactic training, key population Photovoice presentation, and patient case presentation. In addition to addressing HIV testing, prevention, and linkage to care through the presentation of standardized procedures to facilitate education and behavioral design, didactic trainings will include content to increase education surrounding key populations. Weekly Photovoice presentations will facilitate extended contact with key populations and PLWH. Patient-case presentation and discussion will highlight at least one patient from a key population per week, facilitating clinical skills for and changing social norms surrounding working with key populations.*

All phase 4 participants will be invited to complete surveys. A subset of participants (up to 10 per condition) will be invited to participate in focus groups at the end of the intervention.

Citation: Wang, C. C. & Redwood-Jones, Y. A. (2001). Photovoice ethics: Perspectives from Flint photovoice. *Health Education & Behavior*, 28(5), 560-572.

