Phases 2-3: We plan to recruit clinicians by emailing information about the study to members of the Malaysian Medical Association and via established informal networks on social media such as DOBBS (Doctors Only Bulletin Board System) and the Malaysian Primary Care Network. To date, we have had success recruiting Malaysian clinicians via email (participation ranging from 33.4-39.6% of clinicians contacted via email).

Phase 4: We will recruit clinicians from the memberships of the Malaysian Medical Association, Family Medicine Association of Malaysia (FMSA), and Malaysian Primary Care Network. The organizations will share an advertisement to their social media site, which will direct participants to Qualtrics. Participants will be given more information about the study and consent to completing a brief survey and being assigned to a study condition (i.e., step 1 consent). They will then be randomly assigned to a study condition. Clinicians' previous experience with HIV testing will be taken into account in the randomization process to ensure equal distribution of previous experience among study conditions. Once they have been assigned, we will contact them again, provide additional information about their condition, and consent them to the full study (i.e., step 2 consent).

Describe what exclusionary criteria, if any will be applied.

Clinicians who participate in the Phase 3 pre-test will not be eligible to participate in the Phase 4 pilot test.

Describe what (if any) conditions will result in PI termination of subject participation.

N/A

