Phase 4: *Clinicians participating in the intervention pilot will benefit by receiving specialty training in HIV testing, prevention, and linkage to care. We believe that this will be desirable for some because some clinicians volunteer to receive this training via HIV Connect. Additionally, clinicians earn Continuing Medical Education credits after completing each module and assessment of HIV Connect, and a certificate of completion upon finishing all modules and assessments. We will seek approval for the Project ECHO arms to also be eligible for Continuing Medical Education credits, and will amend this protocol to reflect this benefit if our application is approved. Clinicians receive Continuing Medical Education credits for completing Project ECHO in the U.S. and elsewhere.*

Describe any potential future benefits to this class of participants, others, or society.

Clinician stigma remains a potent and persistent driver of disparities in HIV testing, prevention, and linkage to care globally. It is unlikely that we will eliminate these disparities and achieve equity in HIV testing, prevention, and linkage to care until we effectively address clinician stigma. The proposed project will result in important knowledge regarding the acceptability, feasibility, and preliminary impact of a significant and innovative strategy for reducing clinician stigma at large scale: the implementation of evidence-based stigma reduction tools via a popular teletraining platform. In light of the protections that we have in place within our study procedures, we believe that the risks to participants of this project are minimal. We therefore believe that the risks to participants are reasonable in relation to the importance of the knowledge that may be gained from this study.

If there is a Data Monitoring Committee (DMC) in place for this project, please describe when and how often it meets.

N/A

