Phase 4: *Quantitative analyses will be conducted in R version 3.6.2 and include an examination of descriptive statistics and generalized linear models. We will examine changes in mean self-reported stigma (i.e., prejudice, stereotypes, and discrimination) across the 3 time-points of data collection. We will use a two-way repeated measures ANOVA to determine whether any change in stigma is associated with the interaction between the type of condition (factor one) and time (factor two). Qualitative analyses will follow the same*

analytic steps and use the same software as those that we will apply Phases 1-3, except that our analysis will focus on interview transcripts. All qualitative focus groups will be transcribed by our trained research assistants. Results are expected to provide insight into the acceptability and feasibility of the intervention, including barriers to and facilitators of implementation and reasons for withdrawal, as well as participants' perceptions of impact on stigma and care delivery.

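### Optional, low priority: Phase 4 allocation is balanced on prior HIV-testing experience, but no analysis term for it is named; adding one gains 0 to about 3 points of power at almost no cost

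*Combined protocol and SAP*

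**What the plan says.** Section 7 (Study Population and Recruitment, Phase 4) states that "previous experience with HIV testing will be taken into account in the randomization process to ensure equal distribution of previous experience among study conditions". It does not give the method (stratification, blocking or minimisation) or the categories of experience.

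Section 10 (Data, Phase 4) plans this test: "two-way repeated measures ANOVA to determine whether any change in stigma is associated with the interaction between the type of condition (factor one) and time", with stigma measured "across the 3 time-points of data collection". The same paragraph says that the quantitative analyses will "include an examination of descriptive statistics and generalized linear models", but lists no terms for those models. Experience is therefore not named in any model, and it is not ruled out of one either.

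Section 6 (Procedures) assigns 26 clinicians to each of three conditions, 78 in all. Section 8 (Risks and Benefits) says that the project will produce knowledge on the "acceptability, feasibility, and preliminary impact of a significant and innovative strategy for reducing clinician stigma". No alpha, power, effect size or standard deviation is stated.

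**The concern.** When a trial balances allocation on a factor, the usual practice is to analyse by that factor too. Balancing removes the factor from the comparison between arms. If the factor also predicts the outcome, an analysis that ignores it leaves the corresponding variation in the error term, and the test gives up some precision that the design has already paid for.

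In a repeated measures analysis the point is narrower. A stable difference in stigma between experienced and inexperienced clinicians cancels in the within-person contrasts and does not touch the condition-by-time test. Only a difference in how much the two groups change over time stays in the relevant error term. What is at stake is a small amount of precision in the preliminary-impact comparison of a pilot with 26 per arm.

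**Working it through.** There is no power or sample-size figure in the plan to reproduce. The arm sizes agree with the total: 3 × 26 = 78.

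**Inputs from the documents.** 26 per arm, three arms, three time-points, condition-by-time test.

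**Assumed, because the documents are silent.** Alpha 0.05; complete data, independent between participants; compound symmetry with within-person correlation 0.5; outcome SD 1; a 0.6 SD effect in the intervention arm, complete by the second time-point; a two-level experience factor, split equally within each arm; a difference in change *d* between the two levels of 0, 0.3 or 0.5 SD.

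**Degrees of freedom.** The interaction has (3 − 1) × (3 − 1) = 4. Error without the experience-by-time term: (78 − 3) × 2 = 150. With it: (78 − 4) × 2 = 148.

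**Signal.** A time profile of (0, 1, 1) has a centred sum of squares of 2/3. The intervention indicator has a centred sum of squares of 26 × (2/3)² + 52 × (1/3)² = 17.33. The error variance per within-person contrast is 1 − 0.5 = 0.5. The noncentrality is 17.33 × 0.6² × (2/3) / 0.5 = 8.32.

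**Noise added by omitting the factor.** If the difference is common to all arms, the extra error sum of squares is 78 × ¼ × d² × (2/3). At d = 0.5 this is 3.25. Spread over 150 degrees of freedom it is 0.0217, against an error variance of 0.5: an increase of 4.3%.

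A single experience-by-time term removes only the part of the difference that is average across arms. With the difference in both ECHO arms it removes (2/3)² × 3.25 = 1.44; with the difference in the intervention arm only, (1/3)² × 3.25 = 0.36.

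**Power (%), without → with the term** (20,000 simulated trials per cell; mean intervention effect held at 0.6 SD):

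| Difference in change occurs in | d = 0 | d = 0.3 SD | d = 0.5 SD |
|---|---|---|---|
| All arms | 61.1 → 61.0 | 60.0 → 61.0 | 58.2 → 61.0 |
| Both ECHO arms | 61.1 → 61.0 | 60.4 → 60.7 | 59.1 → 60.3 |
| Intervention arm only | 61.1 → 61.0 | 60.8 → 60.7 | 60.2 → 60.4 |

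**Type I error at d = 0.5 SD, without versus with the term.** All arms: 0.042 versus 0.050. Both ECHO arms: 0.045 versus 0.047. Intervention arm only: 0.047 versus 0.047. Omission does not inflate it.

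**Stable difference.** With a 1.0 SD difference in level that does not change over time, power is 61.1% either way.

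**Sensitivity of the gain at d = 0.5 SD.**
- Correlation 0.3 to 0.7: 2.0 to 3.0 points (all arms), 0.9 to 1.3 (both ECHO arms), 0.2 to 0.3 (intervention only).
- Unequal strata, 5 of 26 per arm in one level: 1.7, 0.8 and 0.2 points.
- Other intervention effects, difference common to all arms: about 1.8 points at 0.3 SD (15.5 to 17.2%) and 0.8 points at 0.9 SD (93.5 to 94.3%).
- Effects of 0.6 to 1.0 SD of change that build up linearly, difference common to all arms: 0.5 to 2.0 points for the planned 4-df test. A 2-df test on one change score gives 0.5 to 3.3 points.

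**In clinicians.** In the most favourable case (d = 0.5 SD in all arms), unadjusted power is 57.8%, 59.9% and 61.5% at 26, 27 and 28 per arm, against 60.7% adjusted at 26 (40,000 runs). The gain is worth 1 to 2 clinicians per arm.

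**The case against.** The strongest case against raising this is that no error is shown. The document is an ethics application for a pilot with a one-paragraph analysis summary, it sets no power target, it does not establish that experience predicts change in stigma, and the unspecified generalized linear models could already contain the term. All of that stands, and it is why the point is an option and not a defect.

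A reader might infer that omitting the factor makes the planned test wrong. It does not: omission pushes the type I error down, if anything.

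A reader might equally infer the opposite, that the planned test is therefore sound. The documents do not support that either, because only omission of the balancing factor was examined.
- Section 6 has the ECHO participants meeting every two weeks in a learning community for nine months. Suppose that each ECHO arm is one community and that 1% or 2% of the outcome variance is shared by community and occasion (both assumptions). The nominal 5% test then rejects a true null about 12.8% or 22.2% of the time, with or without the experience term.
- Section 7 places the second consent after allocation and after clinicians are told about their condition. Balance at randomisation need not hold among those analysed.
- Sphericity was assumed in every calculation above.

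The size of the gain also depends on the assumed effect. The 0.6 SD case gives about 60% power, where a change in error variance shows most; the gain is smaller at 0.3 and 0.9 SD. "About 3 points" is the top of a range.

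**Conclusion.** The point holds as an optional, low-priority improvement. The trial balances on experience and names no analysis term for it. Taken alone, this neither biases the condition-by-time test nor inflates its type I error; at most the test is slightly conservative.

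The power to be gained is 0 to about 3 points for differences in change up to 0.5 SD. It is largest near 60% power with a difference common to all arms, about 1 to 2 points at intervention effects of 0.3 or 0.9 SD, and close to nothing if the difference arises only in the intervention arm. Every figure rests on the assumptions listed in the working, none of which the documents supply. The verdict says nothing about clustering, loss after allocation or sphericity.

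**What to change.** Add one sentence to the Phase 4 analysis in section 10: the repeated measures model will include the experience variable used in the randomisation, coded the same way, and its interaction with time. The interaction is the term that matters; a main effect of experience alone does not change the condition-by-time test. Since section 7 gives no categories, the coding used for allocation should be recorded as well.

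No new data or participants are needed, because experience must be known before allocation. A two-level factor takes 2 of the 150 error degrees of freedom. More levels take more: five would leave (78 − 3 − 4) × 2 = 142. If experience is irrelevant, power is essentially unchanged (61.1% versus 61.0% with two levels; 61.2% versus 61.1% with five). Naming the term in advance also removes any appearance of choosing covariates after seeing the data.

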8. RISKS AND BENEFITS

List all potential physical, psychological, social, financial or legal risks to subjects (risks listed here should be included on the consent form).

Phase 1: The most significant potential risk to people at risk of or living with HIV is a breach of confidentiality: Participants may face consequences if others were to learn that they are a member of a population that is at risk for HIV or living with HIV due to their participation in this study. This risk is similar to what participants face in their day-to-day lives through their participation in the organizations from which we will recruit them (i.e., Malaysian AIDS Council, Kuala Lumpur AIDS Support Services Society, and PT Foundation).

Phases 2-4: Risks include the possibility of slight discomfort when considering stigma experienced by key populations and PLWH in clinical settings. Additionally, breaches in confidentiality may result in employment-related repercussions if participants express an unpopular viewpoint. These risks are not expected to be greater than those that participants face in day-to-day lives.

In your opinion, are risks listed above minimal* or more than minimal? If more than minimal, please justify why risks are reasonable in relation to anticipated direct or future benefits.

Phase 1: Given that individuals will only be invited to participate if they are already affiliated with organizations serving men who have sex with men, transgender women, female sex workers, people who inject drugs, and people living with HIV, the risks of participating in this study will be similar to those encountered in these participants' daily lives. We will not recruit participants who are not already affiliated with HIV organizations. Additionally, members of our study team have recruited individuals from these populations for many studies over the last several decades. In this time, there have been no known breaches of confidentiality experienced by research participants. We therefore believe that risks associated with this study are minimal.

Phases 2-4: Experiences of slight discomfort and breaches of confidentiality are risks similar to those faced by clinicians in their everyday lives. We therefore believe that risks associated with these studies are minimal.

(*Minimal risk means the probability and magnitude of harm or discomfort anticipated in the research are not greater than those ordinarily encountered in daily life or during the performance of routine physical or psychological examinations or tests)

What steps will be taken to minimize risks?

Phase 1: We will take several measures to protect members of key populations and PLWH participating in our Photovoice procedures from a breach of confidentiality:

- a. We will not record participants' names at any point during the study. Given that a breach of confidentiality represents the largest risk to participants, we will apply for Institutional Review Board approval to use a consent form that does not require participant signatures. Participant names will not be recorded in affiliation with their Photovoice data. Because we will be working with very small samples of participants (i.e., 6-7 members per key population group), we will not collect socio-demographic data that could be used to identify participants (e.g., age, gender, ethnicity, religion).
- b. The study website is HIPAA-compliant. We consulted with IT experts at the University of Delaware regarding the security of PhotoVoice submissions. Even though we are not collecting HIPAA data, we ultimately decided to build a HIPAA-compliant website because it offers a very high level of security features (similar to those for medical provider websites). All data submitted by study participants will be both encrypted in transit and at rest. Although participants will be required to log into the website to access study materials and submit Photovoice responses, they will not be asked to use their personal email address or any other personally identifiable information to do so. The study team will create and distribute unique login identifiers and passwords to all study participants.
- c. All communication with study participants engaged in the online version of the study will occur via WhatsApp, which offers end-to-end encryption of calls and texts. Thus, communication with study participants will be secure.

- d. We will ensure that photographs do not include identifying information. At the online and in-person Photovoice trainings, [name] will introduce techniques to protect participant identities (e.g., capturing people's shadows rather than faces). Participants will be instructed to not include identifying information in their photographs, and they will be given examples of responses that do not include identifying information (please see submitted examples). Any photographs including identifying information will be destroyed and will not be included in final Photovoice presentations. We have developed a photograph de-identification protocol based on HIPAA guidance and recommendations for de-identifying photographs in medical settings (Nettrour, Burch, & Bal, 2019). Two members of our team will independently review each photograph for four different categories of identifiers (i.e., facial photography, identifiers intrinsic to the participant, identifiers on the participant, and identifiers around the participant). They will report any identifiers on our "photograph de-identification form." Photographs will then be categorized as (1) not including identifiers and thus eligible for inclusion in Photovoice presentations, (2) including identifiers that cannot be edited out and thus must be permanently deleted, or (3) including identifiers that can be edited out and thus will be edited and re-reviewed.
- e. We will not use participants' voices to narrate Photovoice presentations. Participants will develop story scripts to accompany their photograph presentations. Members of the research team will read the story scripts for the final Photovoice presentations, and clinicians will be told that Photovoice narratives are read by actors. Participant voices will not be recorded at any point during the study.
- f. All final Photovoice presentations will be screened to ensure that they include no identifying information. [name], [name], and [name] will choose the Photovoice presentations to be included in the intervention. They will then share these presentations with members of the study team, including Drs. [name], [name], and [name], who will screen the Photovoice presentations for identifying information. If any identifying information is found, the Photovoice presentations will be edited to ensure anonymity.
- g. All electronic data to be analyzed will be stored on a password-protected server with access restricted to members of the study team.

Phases 2-4: To protect clinicians from discomfort, we will emphasize during the informed consent process that they may choose to not engage in conversations that make them uncomfortable, skip survey and/or interview questions, and end the study at any time. To protect clinicians from a breach of confidentiality, we will store all electronic data on a password-protected server with access restricted to members of the study team. Clinicians will be given an alphanumeric participant ID code. All participant data (e.g., survey results) will be stored along with this participant ID, rather than participants' names. The log linking participant IDs with participant names will be stored on a password-protected server with access restricted to members of the study team during the duration of the study. After the study, the log will be destroyed so that there is no record linking participants with their data. Additionally, we will use a HIPAA compliant version of zoom when conducting interviews and focus groups with clinicians. Additionally, participants of the online focus groups (Phase 2) will be able to use a pseudonym instead of the real name while responding to questions.

Nettrour J. F., Burch, M. B., & Bal, B. S. (2019). Patients, pictures, and privacy: Managing clinical photographs in the smartphone era. *Anthroplasty Today*, 57-60.

Describe any potential direct benefits to participants.

Phase 1: Participants may enjoy the opportunity to learn about photography or find the opportunity to document and share their experiences via Photovoice to be fulfilling.

Community groups in which participants are involved may use the Photovoice presentations for advocacy purposes, which could lead to policy changes that benefit the populations that participants represent. Yet, participants are unlikely to personally benefit from participation in this phase.

Phase 2: *Participants may find the opportunity to provide feedback on the intervention to be fulfilling. Yet, participants are unlikely to personally benefit from participation in this phase.*

Phase 3: *Participants may benefit by receiving some limited specialty training in HIV testing, prevention, and linkage to care.*

Phase 4: *Clinicians participating in the intervention pilot will benefit by receiving specialty training in HIV testing, prevention, and linkage to care. We believe that this will be desirable for some because some clinicians volunteer to receive this training via HIV Connect. Additionally, clinicians earn Continuing Medical Education credits after completing each module and assessment of HIV Connect, and a certificate of completion upon finishing all modules and assessments. We will seek approval for the Project ECHO arms to also be eligible for Continuing Medical Education credits, and will amend this protocol to reflect this benefit if our application is approved. Clinicians receive Continuing Medical Education credits for completing Project ECHO in the U.S. and elsewhere.*

Describe any potential future benefits to this class of participants, others, or society.

Clinician stigma remains a potent and persistent driver of disparities in HIV testing, prevention, and linkage to care globally. It is unlikely that we will eliminate these disparities and achieve equity in HIV testing, prevention, and linkage to care until we effectively address clinician stigma. The proposed project will result in important knowledge regarding the acceptability, feasibility, and preliminary impact of a significant and innovative strategy for reducing clinician stigma at large scale: the implementation of evidence-based stigma reduction tools via a popular teletraining platform. In light of the protections that we have in place within our study procedures, we believe that the risks to participants of this project are minimal. We therefore believe that the risks to participants are reasonable in relation to the importance of the knowledge that may be gained from this study.

If there is a Data Monitoring Committee (DMC) in place for this project, please describe when and how often it meets.

N/A

